8.1.3. Other Electronic diary Activities

The following activities are to be completed by the participant on the Electronic diary.

- Prescreening questionnaire
- Consent
- Inclusion/exclusion criteria
- Enrollment
- Demographics
- Enter date and time self-swab #1 and #2 performed.
- Confirm no health events occurred within 12hrs following self-swab #1 and #2.
- Enrollment and end of study questionnaires

The Electronic diary will have the following AE reminders after a swab for the participants:

Report any health events occurring 12hrs following self-swab #1 and #2.
 Instructions and reminders on when and how to report any health events will be given to the participant, as well as a contact telephone number.

The Electronic diary will have the following daily reminders for the participants:

- Remind participant to collect swab if new or increased symptoms occur.
- Remind the participant to call 911 if any medical emergency.
- Remind the participant to complete daily symptom and voice entries on Electronic diary.

8.1.4. Rater Qualifications

Not Applicable

8.1.5. Imaging Assessments

Not Applicable

8.2. Safety Assessments

Unscheduled clinical laboratory measurements or other safety assessments may be obtained at any time during the study to assess any perceived safety issues.

8.2.1. Protocol-Required Clinical Safety Laboratory Assessments

Protocol-required clinical safety laboratory assessments will not be performed in this study.

8.3. Adverse Events and Serious Adverse Events

The definitions of an AE, SAE and research related injury (RRI) can be found in Appendix 2. The investigator is required to assess whether any AE may be related to participation in the study. All AEs (i.e., serious and non-serious, including those attributed to a protocol-required procedure identified as RRI) are collected in the clinical study database. Should a participant, in the investigator's opinion, suffer a medically important research related injury caused by their participation in the study, the designated Pfizer clinician or medical monitor must be notified immediately by telephone or email.

AEs may arise from symptoms or other complaints reported to the Investigator by the participant (or, when appropriate, by a caregiver, surrogate, or the participant's legally authorized representative) or they may arise from clinical findings of the Investigator or other HCPs (clinical signs, test results, etc.).

The investigator and any qualified designees are responsible for detecting, documenting, and recording events that meet the definition of an AE or SAE and remain responsible to pursue and obtain adequate information both to determine the outcome and to assess whether the event meets the criteria for classification as an SAE or caused the participant to discontinue the study intervention (see Section 6.1).

During the active collection period for safety events (see Section 8.3.1), each participant will be questioned about the occurrence of AEs in a nonleading manner.

In addition, the investigator may be requested by Pfizer Safety to obtain specific follow-up information in an expedited fashion.

8.3.1. Time Period and Frequency for Collecting AE and SAE Information

Procedure-Observation Time Table:

| Procedure | Minimum Observation Time for Section 8.3.1. | |
|----------------------------|--|--|
| Nasal self-swab collection | Up-to 12 Hours following swab | |

The time period for actively eliciting and collecting AEs and SAEs ("active collection period") for each participant begins at the time that the nasal self-swab #1 and #2 are performed and ends 12 hours after that procedure/intervention has completed.

The investigator is required to perform appropriate follow-up of each adverse event throughout and after the active collection period and until the AE/SAE or its sequelae resolve or stabilize at a level acceptable to the investigator and Pfizer concurs with that assessment.

If the participant withdraws from the study and also withdraws consent for the collection of future information, the active collection period ends when consent is withdrawn.

If a participant definitively discontinues or temporarily discontinues study intervention because of an AE or SAE, the AE or SAE must be recorded on the CRF and the SAE reported using the NIS AE Report form.

Since there is no product under study, there is no post-study active reporting period for the SAEs to be communicated to Pfizer Safety.

Symptoms of respiratory illness will be collected from the time of consenting to the clinical research through the end of the study daily through the Electronic diary. This information will not be reported on an AE CRF unless that they occur within the 12 hrs following swab.

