1.3. Schedule of Activities

The SoA table provides an overview of the protocol visits and procedures. Refer to the STUDY ASSESSMENTS AND PROCEDURES section of the protocol for detailed information on each procedure and assessment required for compliance with the protocol.

The investigator may schedule visits (unplanned visits) in addition to those listed in the SoA table, in order to conduct evaluations or assessments required to protect the well-being of the participant.

| Visit Identifier | Screening (Day 1) | Enrollmen t (Day 1 + 1 day) | Self-swab #1 (Day 2 + 6 days) | Self-swab #2 Symptomati c participants (Day 2 + 40 days) | Self-swab #2 Asymptomati c participants (Day 42 +1 days) | Extended electronic diary Only for virus positive participants ^f (Day 42 to 56) |
|--|-------------------|--------------------------------------|--|---|---|--|
| Informed consent | X | | | | | |
| Inclusion and exclusion criteria | X | | | | | |
| Access Electronic diary | | X | | | | |
| Demography | | X | | | | |
| Enrollment Questionnaire | | X | | | | |
| (includes self-reported medical | | | | | | |
| history) | | | | | | |
| Daily symptom and voice entry on the Electronic diary | | X | \rightarrow | \rightarrow | \rightarrow | \rightarrow |
| Obtain SARS-CoV- | | | Xa | X ^b | X° | |
| 2/influenzavirus/RSV nasal | | | | | | |
| self-swab | | | | | | |
| Enter date and time of self- | | | X | X | X | |
| swab when completed in | | | | | | |
| Electronic diary | | | | | | |

PFIZER CONFIDENTIAL

| Visit Identifier | Screening | Enrollmen | Self-swab | Self-swab #2 | Self-swab #2 | Extended electronic |
|--------------------------------|-----------|------------|---------------|---------------|---------------------------|---------------------------|
| | | t | #1 | Symptomati | Asymptomati | diary |
| | | | | С | С | Only for virus positive |
| | | | | participants | participants | participants ^f |
| | (Day 1) | | | | | |
| | | (Day 1 + 1 | (Day 2 + 6 | (Day 2 + 40 | (Day 42 +1 | (Day 42 to 56) |
| | | day) | days) | days) | days) | |
| Confirm no AE's 12 hours after | | | X | | X | |
| self-swab; enter date and time | | | | | | |
| in Electronic diary | | | | | | |
| End of Study Questionnaire | | | | | $\mathbf{X}^{\mathbf{d}}$ | Xe |
| Collect AEs and RRIs as | X | X | \rightarrow | \rightarrow | \rightarrow | \rightarrow |
| appropriate | | | | | | |

- a. Participant is required to perform self-swab #1 as soon as possible once they receive the collection kit.

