8.1.2. Nasal Self-swab

Participants will need to complete two nasal self-swabs.

Collection of Self-swab #1

Participants will need to perform Self-swab #1 as soon as possible, once they receive the home collection kit.

The collection of Self-swab #2 might occur at 2 different points in the study:

- a) If participant develops new or increased symptoms, the participant will perform Self-swab #2 (after Self-swab #1 and before day 42). Self-swab #2 Criteria: An illness involving any 1 or more of the following symptoms will trigger self-swab collection:
 - New or increased fever
 - New or increased cough
 - New or increased shortness of breath or difficulty breathing.
 - New or increased fatigue
 - New or increased nasal congestion
 - · New or increased runny nose
 - · New or increased sore throat
 - New or increased loss of taste or smell
 - New or increased chills
 - New or increased rigors
 - New or increased muscle pain
 - New or increased diarrhea
 - New or increased vomiting
 - New or increased headache
 - New or increased nausea
 - New or increased wheezing
- b) If participant does not develop any new or increased symptoms, the participant will be asked to self-swab at day 42.

Detailed instructions on collection, processing, storage, and shipment for the nasal self-swab and contact information will be provided to the participant.

Depending on the results of the self-swab, the following results will determine the end of study for the participant (positive and negative refer to all viruses tested):

- a) All negative or invalid results from self-swab #1 and #2, the participant will stop the study at approximately the end of week 6.
- b) Any positive self-swabs #1 or #2, the participant will continue the study until end of Week 8.
- c) If both self-swabs are invalid the participant will exit the study at approximately the end of Week 6.

d) If one self-swab is negative and another is invalid, the participant will exit the study at approximately the end of Week 6.

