10.2.1. Definition of AE

AE Definition

- An AE is any untoward medical occurrence in a patient or clinical study participant, temporally associated with a study intervention, whether or not considered related to the study intervention.
- NOTE: An AE can therefore be any unfavorable and unintended sign (including an abnormal laboratory finding), symptom, or disease (new or exacerbated) temporally associated with a study intervention.

Events Meeting the AE Definition

- Any abnormal laboratory test results (hematology, clinical chemistry, or urinalysis) or
 other safety assessments (e.g., ECG, radiological scans, vital sign measurements),
 including those that worsen from baseline, considered clinically significant in the
 medical and scientific judgment of the investigator. Any abnormal laboratory test
 results that meet any of the conditions below must be recorded as an AE:
 - Is associated with accompanying symptoms.
 - o Requires additional diagnostic testing or medical/surgical intervention.
 - Leads to a change in the study intervention schedule (outside of any protocol-specified adjustments) or discontinuation from the study, significant additional concomitant drug treatment, or other therapy.
 - Exacerbation of a chronic or intermittent preexisting condition including either an increase in frequency and/or intensity of the condition.
 - New conditions detected or diagnosed after study intervention administration even though it may have been present before the start of the study.
 - Signs, symptoms, or the clinical sequelae of a suspected drug interaction.
 - Signs, symptoms, or the clinical sequelae of a suspected overdose of a concomitant medication. Overdose per se will not be reported as an AE/SAE unless it is an intentional overdose taken with possible suicidal/self-harming intent. Such overdoses should be reported regardless of sequelae.

Events **NOT** Meeting the AE Definition

 Any clinically significant abnormal laboratory findings or other abnormal safety assessments which are associated with the underlying disease, unless judged by the investigator to be more severe than expected for the participant's condition.

PFIZER CONFIDENTIAL

- The disease/disorder being studied or expected progression, signs, or symptoms of the disease/disorder being studied, unless more severe than expected for the participant's condition.
- Medical or surgical procedure (e.g., endoscopy, appendectomy): the condition that leads to the procedure is the AE.

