6.6. Safety Summaries and Analyses

The safety analysis set is the FAS. The incidence and severity of adverse events (AEs)/research related injuries (RRIs) will be summarized according to Pfizer standards.

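### The planned AE incidence over all enrolled participants does not isolate the effect of the self-swab: the recording rules conflict for a symptomatic swab #2, and the denominator includes people who never swabbed

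*Protocol*

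**What the plan says.** **Window.** Protocol 8.3.1 ties active AE collection to the swabs: the period "begins at the time that the nasal self-swab #1 and #2 are performed and ends 12 hours after that procedure/intervention has completed". Diary symptoms of respiratory illness are kept apart from AE reporting, with one exception: "This information will not be reported on an AE CRF unless that they occur within the 12 hrs following swab".

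**Trigger for swab #2.** Protocol 8.1.2: "An illness involving any 1 or more of the following symptoms will trigger self-swab collection". Sixteen symptoms follow, among them runny nose, congestion, sore throat and cough.

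**AE definition.** Protocol 10.2.1 lists among events that are not AEs: "The disease/disorder being studied or expected progression, signs, or symptoms of the disease/disorder being studied, unless more severe than expected". Section 8.3.1.2 refers to Appendix 2 for which events go on the CRF. Section 8.3.7, the heading for disease-related events that do not qualify as AEs, is marked not applicable.

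**The 12-hour check.** The Schedule of Activities (1.3) has a row beginning "Confirm no AE's 12 hours after", marked for swab #1 and the asymptomatic swab #2 only. Protocol 8.1.3 asks participants to do the following, without exception: "Confirm no health events occurred within 12hrs following self-swab #1 and #2".

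**Analysis.** The endpoint in Protocol 3 and SAP 3.5 is AE/RRI incidence and severity among all enrolled. SAP 6.6: "The safety analysis set is the FAS". SAP 4 defines the FAS by consent and enrolment. Layout is left to sponsor standards, and the supplied text specifies no split by swab or by the reason for it.

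**The concern.** A swab-safety rate should count events that could follow from the swab, among people who took one. The plan departs from this on both sides of the fraction.

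In the numerator, a symptomatic swab #2 is taken because the participant is ill. Whether that illness is counted as an AE depends on whether the site follows 8.3.1 or Appendix 2. Some trigger symptoms, such as runny nose or sore throat, could also plausibly follow nasal swabbing, so the two sources are hard to separate afterwards. The blank Schedule cell gives sites a second reason to handle this swab differently from the others.

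In the denominator, a participant who never swabs has no active collection window but still counts.

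At stake is whether the reported incidence can be read as a property of the swab. No efficacy conclusion or stopping decision is involved.

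**Working it through.** The documents state no AE rate, swab completion rate or safety precision target, so there is no figure of the plan to reproduce. The check sets the passages side by side and then illustrates size.

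**1. Recording rule.** Take a participant whose new cough triggers swab #2 and who still reports the cough in a diary entry within 12 hours.
- 8.3.1 can be read as sending the cough to the AE CRF.
- 10.2.1 keeps it off, unless it is more severe than expected.
- 8.3.1 speaks of symptoms that occur after the swab. Whether a symptom already present at swabbing qualifies is not defined, and the diary is scheduled once a day.

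**2. Schedule row.** The extracted row reads "Confirm no AE's 12 hours after | | | X | | X". The columns are screening, enrolment, swab #1, symptomatic swab #2, asymptomatic swab #2 and extended diary, so the blank between the two marks is the symptomatic swab #2. The rows for taking the swab and for entering its date and time are marked in all three swab columns, so a reading fault is unlikely.

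**3. Denominator.** Let s be the share of enrolled who swab at least once (assumed) and p the AE rate among them. If AEs come only from those who swab:

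FAS rate = p × s; relative understatement = 1 − s.

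| s (assumed) | Swabbed, of 8,700 | FAS rate if p = 1% | Understated by |
|---|---|---|---|
| 90% | 7,830 | 0.9% | 10% |
| 70% | 6,090 | 0.7% | 30% |
| 50% | 4,350 | 0.5% | 50% |

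**4. Illness symptoms counted as AEs.** Let a be the true swab AE risk per swabbed participant, q the share of swabbed participants who take a symptomatic swab #2, and r the share of those whose illness symptom is recorded as an AE. All are assumed, and the two event types are taken as independent:

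P(any AE | swabbed) = 1 − (1 − a)(1 − q × r).

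With a = 1%:

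| q | r | Calculation | Rate among swabbed | FAS rate, s = 70% |
|---|---|---|---|---|
| any | 0 | 1 − 0.99 × 1 | 1.0% | 0.7% |
| 10% | 10% | 1 − 0.99 × 0.99 | 2.0% | 1.4% |
| 30% | 50% | 1 − 0.99 × 0.85 | 15.9% | 11.1% |
| 50% | 100% | 1 − 0.99 × 0.50 | 50.5% | 35.4% |

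The two effects oppose each other. The width of the second range reflects ignorance of q and r. It is not a forecast.

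**The case against.** A reader might infer that swab safety cannot be described at all. The documents do not support that. Protocol 8.3 requires a relatedness assessment for every AE and identifies procedure-attributed events as RRIs. SAP 6.6 summarises RRIs. SAP 6.2.4.1 counts who took swab #1, swab #2 and both. The material for a usable summary is collected; what the supplied text lacks is its specification.

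A reader might also infer that a symptomatic swab #2 has no active AE check. That fails too. Sections 8.1.3 and 8.3.1 cover both swabs, and the Schedule's general AE/RRI row runs through every column. The blank cell is an inconsistency, not an absence of collection.

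Nor were unswabbed participants wholly unobserved. The general row starts at screening, and 10.2.3 has events outside the window recorded if suspected to be procedure-related. Only active elicitation depends on a swab.

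Three further points stand in part:
- Section 8.3.1.2 refers to Appendix 2, which suggests that the appendix governs. But 8.3.1 carries its own express exception, and 8.3.7, where the matter could have been settled, is not applicable.
- All enrolled is the stated endpoint population, so it is a choice that SAP 6.6 follows correctly. That argues for adding a summary rather than replacing one.
- Sponsor standards may already include a relatedness split. They are not in the documents. Causality also helps less where it is uncertain, because 10.2.3 has an event of unknown cause treated as related for reporting.

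**Conclusion.** The concern holds in a limited form: the planned all-cause AE incidence over all enrolled participants does not isolate the effect of the self-swab. The textual conflicts (8.3.1 with 10.2.1, and Schedule 1.3 with 8.1.3 and 8.3.1) need no assumptions. The dilution equals the unswabbed share, provided recorded AEs arise only among those who swab; its size, 10% to 50% relative, rests on assumed swab rates of 90% to 50%. Inflation by illness symptoms depends on which recording rule sites follow and could be absent or much larger than the dilution, so the direction of the net error is unknown. Severity is minor to moderate: the procedure is low-risk, the objective is descriptive and no decision depends on it.

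**What to change.** **Protocol.** Reconcile the Schedule of Activities (1.3), 8.1.3, 8.3.1, 8.3.7 and 10.2.1 so that one recording rule and one 12-hour check apply to every swab occasion. State whether a symptom already present at swabbing counts as occurring in the window. Which rule to adopt is for the sponsor to decide.

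**SAP 6.6.** Keep the all-enrolled summary, which matches the endpoint. Add AEs and procedure-related AEs/RRIs:
- among participants with at least one swab, counted without the exclusion for operational errors that SAP 6.2.4.1 applies;
- by occasion: swab #1, symptomatic swab #2 and asymptomatic Day 42 swab #2;
- with the listed illness symptoms after a symptomatic swab on a separate line.

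**Cost.** A protocol clarification and a few extra tables. Swab date and time are already entered in the diary, but the documents list no field for the reason for swab #2, so it must be derived from diary symptoms and dates. The derivation needs a written rule, because the trigger in 8.1.2 is any single symptom while onset in SAP 5.2.2.1 uses the total score, and the two can disagree. Per-swabbed rates will be higher than FAS rates wherever some participants do not swab, and the report should say why.

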8.3.1.1. Reporting SAEs to Pfizer Safety

All SAEs occurring in a participant during the active collection period (see Section 8.3.1) are reported to Pfizer Safety on the NIS AE Report form immediately upon awareness, as indicated in Appendix 2; under no circumstance should the time between awareness and reporting of the SAE exceed 24 hours. The investigator will also submit any updated SAE data to the sponsor within 24 hours of it being available.

Reportable SAEs include events related to an approved Pfizer product taken by the participant under routine care, during the time they are participating in the study, should such events come to the attention of the Investigator (including an overdose or a medication error that led to the SAE). Refer to Appendix 2 for the definition of an overdose or medication error.

8.3.1.2. Recording Nonserious AEs and SAEs on the CRF

All applicable SAEs and nonserious AEs, as described in Appendix 2, that are directly observed and/or spontaneously reported by the participant during the active collection period (described in Section 8.3.1) will be recorded on the AE page of the CRF.

8.3.2. Method of Detecting AEs and SAEs

The method of recording, evaluating, and assessing causality of AEs and SAEs and the procedures for completing and transmitting SAE reports are provided in Appendix 2.

Care will be taken not to introduce bias when detecting AEs and/or SAEs. Open -ended and nonleading verbal questioning of the participant is the preferred method to inquire about AE occurrences.

8.3.3. Follow-up of AEs and SAEs

After the initial AE/SAE report, the investigator is required to proactively follow each participant at subsequent visits/contacts. For each event, the investigator must pursue and obtain adequate information until resolution, stabilization, the event is otherwise explained, or the participant is lost to follow-up (as defined in Section 7.2).

In general, follow-up information will include a description of the event in sufficient detail to allow for a complete medical assessment of the case and independent determination of possible causality. Any information relevant to the event, such as concomitant medications and illnesses, must be provided. In the case of a participant death, a summary of available autopsy findings must be submitted as soon as possible to Pfizer Safety.

Further information on follow-up procedures is given in Appendix 2.

8.3.4. Regulatory Reporting Requirements for SAEs

Prompt notification by the investigator to the sponsor of an SAE is essential so that legal obligations and ethical responsibilities towards the safety of participants and the safety of a study intervention under clinical investigation are met.

The sponsor has a legal responsibility to notify both the local regulatory authority and other regulatory agencies about the safety of a study intervention under clinical investigation. The sponsor will comply with country -specific regulatory requirements relating to safety reporting to the regulatory authority, IRBs/ECs, and investigators.

8.3.5. Exposure During Pregnancy or Breastfeeding, and Environmental Exposure

The requirements for reporting pregnancy or breastfeeding and environmental exposure apply throughout the entire active collection period and are outlined below; when such reports are required per protocol, the report must be transmitted to Pfizer Safety within 24 hours of investigator awareness.

